1.0 Objectives

Primary Aim: To determine whether synthetic retropubic midurethral sling (MUS) combined with concomitant detrusor injections of onabotulinumtoxinA is more effective than midurethral sling alone in improving mixed urinary incontinence (MUI) symptoms.

Secondary Aims:

a. To compare incontinence episode frequency on a 3-day diary in women who undergo midurethral sling plus onabotulinumtoxinA to those who undergo midurethral sling alone.

b. To compare urinary incontinence symptoms and quality of life in women who undergo midurethral sling plus onabotulinumtoxinA to those who undergo midurethral sling alone.

c. To identify baseline factors associated with persistent urgency incontinence in women after midurethral sling alone and midurethral sling plus onabotulinumtoxinA.

Hypotheses:

1. By using a double-blind randomized controlled trial, we will be able to show that retropubic midurethral sling surgery with detrusor muscle onabotulinumtoxinA injection will be more effective at controlling mixed urinary incontinence symptoms than sling surgery alone.

2. Patients who receive both midurethral sling and onabotulinumtoxinA injection will have objectively have fewer incontinence episodes than those who receive midurethral sling alone

3. Patients who receive both treatments will have better quality of life as it relates to urinary symptoms than those who receive midurethral sling alone

4. Patients who have persistent urgency urinary incontinence after either midurethral sling alone or both midurethral sling and onabotulinumtoxinA injection alone will have significantly different baseline urine microbial content than those who do not have persistent urgency symptoms after treatment

2.0 Background

Project Abstract:

This double-blind randomized controlled trial looks to find a better treatment for women with mixed urinary incontinence. The primary aim of this study is to determine whether midurethral sling, the predominant incontinence surgery performed worldwide, combined with injections of onabotulinumtoxinA (Botox®) into the large muscle of the bladder improves symptoms of mixed urinary incontinence better than sling surgery alone. Secondary aims are to

compare objectively the frequency of incontinence episodes in patients who receive onabotulinumtoxinA injection versus those who do not. We will also compare urinary incontinence symptoms and quality of life measures in patients who receive the injections versus those who do not. Lastly, we plan to try to identify baseline factors associated with persistent urgency urinary incontinence in women after sling surgery alone and sling surgery plus injection.

We plan to enroll women who have mixed urinary incontinence and randomize them into either treatment with sling surgery alone or sling surgery with bladder onabotulinumtoxinA injection at the time of surgery. Patients will then be followed with scheduled, in-person follow-up with a physician at 2weeks, 3-months and at 1 year. During these visits and prior to surgery, the patients will complete standardized surveys on urinary symptoms, quality of life, pelvic floor function, and sexual health. A urine sample will also be collected from each patient for a detailed analysis of the microbial content that is beyond the scope of a normal hospital laboratory.

After this study, we hope to have developed a new and better treatment for mixed urinary incontinence that can be provided to women suffering with this malady both nationally and internationally. There is currently no standard of care for treatment of mixed urinary incontinence and we aim to provide this to the urogynecologic community. Additionally, differentiating those patients who will have persistent or worsening urgency urinary incontinence after sling surgery from those who have improvement in symptoms has been difficult. By examining the detailed microbial content of participants' urine, we hope to better understand this phenomenon.

Project Background:

Mixed urinary incontinence (MUI) is a clinical conundrum for providers and patients alike. The International Continence Society defined MUI as "involuntary loss of urine associated with urgency or urgency incontinence AND urine loss associated with physical exertion, sneezing or coughing or stress incontinence". While some women ONLY experience one type of incontinence (stress OR urgency), many experience leakage with both, and it is unclear if these MUI symptoms are one disease with a continuum of symptoms or two separate diseases making treatment algorithms challenging. Despite our lack of understanding regarding the disease process or optimal treatment, MUI accounts for up to 50% of incontinence in women. The annual burden of MUI on the national economy is significant and growing.

More importantly, women with MUI are more bothered and suffer more dramatic quality of life impact. Yet, optimal treatments for MUI lag behind. Definitive treatments for stress incontinence are typically surgical, while those for urgency incontinence are behavioral or medical. As early as the 1980s, investigators sought to determine if surgical or non-surgical treatments should be used first for MUI. In one small trial, women with MUI were randomized to medical treatment (e.g. anticholinergic medications designed to relax the bladder muscle) for urgency incontinence or surgery for stress incontinence. Forty-three percent of women in the medicine group continued to have incontinence symptoms, while

only 12-13% of the surgical patients had persistent incontinence symptoms. Further complicating treatment decisions, continence procedures designed to treat stress incontinence have historically worsened urgency incontinence in some women.

There is no high-quality evidence or consensus amongst specialists on how to approach treatment for women with MUI. The optimal treatment strategy for women with MUI is unclear. Historically, health care providers tried to identify which type of incontinence, stress or urgency, was most bothersome to the patient and treated the bothersome subtype first. Those with stress predominant incontinence underwent surgery, while those with urgency predominant incontinence received medications and behavioral/physical therapy. Currently, the primary surgical treatment of stress incontinence is midurethral slings. Greater than 66% of women undergoing midurethral sling surgery for stress incontinence also report baseline urgency incontinence. Investigators report improvement in urgency incontinence in some women with MUI undergoing midurethral sling, however, subjective outcomes are worse in women with MUI compared to pure stress incontinence and the lower cure rates are associated with persistent urgency incontinence. Studies also demonstrated that urgency incontinence is the major cause of patient dissatisfaction of surgery for stress incontinence and prolapse. Reduced satisfaction and treatment failure after midurethral sling surgery is associated with higher baseline urgency and urgency incontinence. Additionally, one study showed that 33% of women who did not have urgency incontinence symptoms prior to midurethral sling developed urgency symptoms after surgery. This study further complicates the issue, as it is possible that midurethral sling may cause urgency symptoms in some patients. Overall, studies have shown a wide range in improvement of urgency incontinence symptoms after midurethral sling placement between 46-74%. The wide range of anticipated improvement coupled with the not insignificant rate of de novo in urgency incontinence symptoms after midurethral sling, make counseling women with MUI contemplating surgery challenging. Essentially, surgeons can counsel women with MUI that although their stress incontinence symptoms are likely to improve after midurethral sling (90% satisfaction), their urgency incontinence may get better, stay the same, or get worse. Other strategies for treating MUI have also been proposed including treatment with anticholinergic medication in addition to traditional sling surgery. In an AHRQ funded study, anticholinergic medical therapy had minimal to moderate efficacy for treatment of urgency incontinence symptoms. Furthermore, many women taking anticholinergic medications suffer bothersome side effects, such as dry mouth and constipation, and over 50% stop taking the medication during their treatment course. In our prior work, we found that women treated with anticholinergic medications prior to traditional continence surgery were more likely to have urgency symptoms post-operatively, suggesting poorer outcomes in women with MUI. Understandably, patients with persistent urgency symptoms post-operatively are significantly less satisfied with their symptoms and surgical outcomes than patients who have complete resolution of their symptoms.

Given the known treatment shortcomings of anticholinergic medications for treatment of urgency incontinences, clinician-investigators began injecting onabotulinumtoxinA into the bladder in an attempt reduce urgency incontinence while minimizing side effects. OnabotulinumtoxinA is a neurotoxin, which inhibits acetylcholine release and temporarily relaxes the bladder muscle to inhibit urgency incontinence. A large NIH funded multicenter double-blind randomized controlled trial investigated the role of detrusor injections with 100 units of onabotulinumtoxinA compared to anticholinergic medications for the treatment of urgency incontinence. More women in the onabotulinumtoxinA group were completely dry (no incontinence episodes) without having the bothersome side effects of the anticholinergic medications. Women in the onabotulinumtoxinA group also had higher rates of transient urinary retention requiring selfcatheterization and urinary tract infection; however, these rates were significantly lower than earlier studies using higher doses of onabotulinumtoxinA. Several studies suggest the optimal dose of onabotulinumtoxinA, which maximized resolution of urinary incontinence while minimizing complications, is 100 units per injection. As a result, onabotulinumtoxinA injections are a standard treatment for urgency incontinence.

Given the superior efficacy and side effect profile of onabotulinumtoxinA and the high rates of persistent urgency incontinence and dissatisfaction after sling surgery in women with MUI, we hypothesize that a combined treatment approach for women with MUI is superior to simply treating the stress incontinence alone. Specifically, women with MUI undergoing sling plus intradetrusor onabotulinumtoxinA will have fewer bothersome incontinence symptoms than women undergoing sling alone. The aim of this double-blind randomized comparative efficacy trial is to determine if women with MUI planning sling surgery sustain greater improvement in their urinary symptoms with the addition of onabotulinumtoxinA injection at the time of sling.

A secondary aim is to identify subsets of women who may be prone to persistent urinary symptoms after treatment. Although classic teaching is that the urine is 'sterile', recent studies identified that urine of normal asymptomatic women contain bacteria; in other words, similar to all other organ systems in the body (gastrointestinal tract, skin, etc) urine is NOT sterile rather it has a microbiome. Recent data suggests that patients with urgency symptoms have a different bladder microbiome (different bacteria) than those who do not suffer from this ailment. Our unit recently found that the microbiome of women with urgency and bladder pain differs from age-matched controls.

3.0 Inclusion and Exclusion Criteria

All women with MUI planning surgical intervention with midurethral sling will be approached for study participation. MUI will be defined as an answer of "moderately' or "quite a bit" bothered to Urinary Distress Inventory (UDI) items (2) "urine leakage with a feeling of urgency" AND (3) "urine leakage related to coughing, sneezing, or laughing". $PROTOCOL \ TITLE: \ \text{The SLIM Study: } \underline{Sl} \text{ing and Botox} \\ \textcircled{B} \ \underline{Injection for } \underline{M} \text{ixed Urinary Incontinence}$

Enrolled participants must meet all the following criteria:

- Undergoing mid-urethral sling surgery
- Have symptoms of both stress and urgency urinary incontinence
- Able to consent, fill out study documents, and complete all study procedures and follow-up visits
- At least 18 years of age
- English speaking
- Be able and willing to learn clean intermittent self catheterization technique

Women will be excluded for any of the following reasons:

- History of recurrent UTI (defined as three culture proven UTIs within last 12 months)
- Systemic neuromuscular disease known to affect the lower urinary tract
- Undergoing concomitant prolapse surgery
- Previous incontinence surgery
- Treatment with anticholinergic medication in the last 2 months
 - Darifenacin/Enablex
 - Oxybutynin IR/Ditropan
 - Oxybutynin ER/Ditropan XL
 - Oxybutynin Patch/Oxytrol
 - Oxybutynin Gel/Gelnique
 - Solifenacin/Vesicare
 - Tolterodine IR/Detrol
 - Tolterodine ER/Detrol LA
 - Trospium IR/Sanctura
 - Trospium ER/Sanctura XR
 - Fesoterodine/Toviaz
 - Mirabegron/Myrbetriq
- Previous bladder injection with onabotulinumtoxinA
- Prisoner status
- Pregnancy
- Patients on SGLT2 Inhibitors
 - (canagliflozin, dapagliflozin, and empagliflozin)

4.0 Study Timelines

Individuals will participate and remain enrolled in the study for approximately 1 year or until they have completed their one year postoperative visit.

We estimate that it will take two years to enroll the total number of subjects required to complete this study.

We expect to be able to complete primary analyses of this study 3 years from the date of IRB approval.

5.0 Study Endpoints

Primary endpoint will occur at 3 months. Secondary endpoint is at 1 year, or when the subject completes her 1 year post-operative visit.

6.0 **Procedures Involved**

Women with MUI undergoing midurethral sling for bothersome SUI will be randomized to 100 units onabotulinumtoxinA or placebo (saline) injections in the detrusor at the time of sling surgery. Specifically, the retropubic midurethral slings used will be either the Gynecare TVT Exact Continence System by Ethicon or the Boston Scientific Advantage Fit Transvaginal Mid-Urethral Sling System based on surgeon preference. Surgeons and participants will be masked to study assignment. Primary outcome will be the Patient Global Assessment of Improvement (PGI-I), a global, patient oriented measure that assesses symptoms of SUI and UUI at 3-months. The primary outcome, PGI-I asks subjects to best describe how their urinary tract condition is now, compared to how it was before treatment for urinary leakage. Response choices are: (1) 'very much better', (2) 'much better', (3) 'a little better', (4) 'no change', (5) 'a little worse', (6) 'much worse', and (7) 'very much worse'. Construct validity of the PGI-I was demonstrated in incontinence trials.32

We selected a subjective, patient oriented outcome as our primary outcome measure secondary to the complex nature of MUI, and the association between dissatisfaction after incontinence surgery and persistent or new onset urgency. We felt the patient's overall impression of their continence status represented a more clinically meaningful outcome than traditional objective measures. In addition, we will compare subjective and objective urinary symptoms and quality of life amongst treatment groups 3-months and 1-year after surgery.

All women with MUI planning surgical intervention with midurethral sling will be approached for study participation. MUI will be defined as an answer of "moderately' or "quite a bit" bothered to Urinary Distress Inventory (UDI) items (2) "urine leakage with a feeling of urgency" AND (3) "urine leakage related to coughing, sneezing, or laughing".

Women will undergo standardized urologic evaluation at baseline including assessment of urinary symptoms and quality of life using short forms of the Urinary Distress Inventory (UDI-6) and Incontinence Impact Questionnaire (IIQ-7); assessment of overall severity of their incontinence symptoms with the Patient Global Impression of Severity (PGI-S);32 post void residual urine volume; urine analysis and culture; multichannel urodynamic testing; and pelvic exam with prolapse quantification using pelvic organ prolapse quantification system (POP-Q)33. All patients will also complete a 3-day urinary diary at baseline quantifying the number of incontinence episodes (stress and urge). Three months and 1-year after surgery, patients will again complete all baseline measures, including UDI, IIQ, PGI-I, PGI-S, and 3-day diary to report symptom and objective urinary symptoms after treatment. A sample of urine will be obtained for microbiome analysis at each visit.

Scheduled in-person follow-up visits will occur at baseline, 2 and 6-weeks, 3-months, and 1-year after surgery. At the baseline, 3-month, and 1-year visits,

 $PROTOCOL \ TITLE: \ \text{The SLIM Study: } \underline{Sl} \text{ing and Botox} \\ \textcircled{B} \ \underline{Injection for \ \underline{M} ixed \ Urinary \ Incontinence}$

research staff will collect the 3-day diary information and record any adverse events that have occurred during the post-operative period. Subjects will also complete the general and condition specific symptom and QOL questionnaires. In addition, an update of current medication and assessment as to whether any evaluation or treatment for pelvic floor disorders or adverse outcomes from surgery have occurred since the previous evaluation will be assessed by clinical staff at the in-person visits. All patient and survey data will be recorded in RedCAP.

7.0 Data and Specimen Banking

Data will be collected at Northwestern Medicine. All study data will be recorded on Case Report Forms by research coordinator and securely maintained in a locked cabinet. CRFs will be derived from source documentation and/or participant self-report. Data will be entered by the research coordinator at Northwestern into a REDCap database that will be stored on a secure sever at the Data Coordinating Center. All collected data must be entered into REDCap within 5 business days. Any queries to data entered into REDCap will be addressed by site staff within 5 business days. It is each site's responsibility to regularly check REDCap for data queries.

Both data and specimens will be banked for further use. Patient specimens will not have any directly identifiable patient information on them, but will remain coded for future studies if the specimen is unused in this study. Argonne National Laboratories will have no access to any patient identifying information. All patient identifiers will be removed prior to transferring microbiome samples to Argonne National Laboratories for processing.

8.0 Data and Specimen Management

All analyses will be conducted using SPSS version 20 (Chicago, IL). Histograms will be used to determine distribution of data and appropriate non-parametric or parametric tests will be selected. Primary outcome will be analyzed dichotomously with responses of "very much better" and "much better" considered an optimal outcome. A chi-square test of association will be used to compare primary outcome (PGI-I) between treatment groups. Questionnaire data will be compared between sling alone and sling plus onabotulinumtoxinA groups using Mann Whitney test. All test results will be considered significant with a p-value of less than or equal to 0.05.

In a study of women with MUI undergoing retropubic midurethral sling, 66% of patients reported a PGI-I of "very much better' or 'much better' at 3-months.23 Similarly, in a randomized trial of intravesical onabotulinumtoxinA 55% of participants had PGI-I scores of "very much better' or 'much better'. Therefore, assuming "optimal outcomes' (PGI-I scores of "very much better' or 'much better' or 'much better) in 66% of women undergoing sling alone and 93% in those undergoing sling plus onabotulinumtoxinA, we will need to recruit 34 patients in each group

to show a significant difference with 80% power at a 0.5 significance level. Assuming a significant attrition rate, we will recruit approximately 100 women (50 in each arm).

Data will be collected at Northwestern Medicine. All study data will be recorded on Case Report Forms by research coordinator and securely maintained in a locked cabinet that only the study coordinator has access to. CRFs will be derived from source documentation and/or participant self-report. Data will be entered by the research coordinator at Northwestern into a REDCap database that will be stored on a secure sever. Only study staff will have passwords to access the project data on REDCap.

The data that is banked locally will be entered into an electronic data capture website. All users of REDCap need an institutional username and password to log in and to enter data. Research personnel, including study staff as well as study doctors will be able to collect and have access to subject data.

All specimen collected will be stored locally in the clinic storage facility until patient de-identification and subsequent transfer to Argonne National Laboratory for analysis can be completed. Any specimens that are not used for this study will be stored for future study use. Only the study coordinator and physicians participating in the study directly will have access to the storage facility for the purposes of adding specimens and sending them out only. Specimens will be batch-shipped to Argonne National Laboratories when enough have accumulated to do so.

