## Statistical Analysis Plan

We based the sample size estimation off of previous studies assessing treatment of slings for mixed urinary incontinence and onabotulinumtoxinA injections for overactive bladder. A PGI-I response at 3 months postoperatively of "very much better" or "much better" was designated "improved." Assuming 66% of women in the placebo group and 93% in the onabotulinumtoxinA group were "improved" based on overall PGI-I scores, 68 women (34 in each arm) were needed to show a significant difference with 80% power at 0.05 significance level. If we assumed a 15% dropout rate, we aimed to recruit 78 participants (39 in each arm). R 3.6.3 was used for statistical analysis of the deidentified data. Independent samples t test, Mann-Whitney, x2, Wilcoxon signed rank sum statistical tests were used as appropriate.

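### The planned chi-square on PGI-I is valid, but the plan leaves unused a baseline urgency measure that the protocol links to treatment failure; one prespecified adjusted analysis is a cheap, modest improvement

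*Protocol*

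**What the plan says.** Protocol section 8.0 dichotomises the primary outcome ("Primary outcome will be analyzed dichotomously with responses of 'very much better' and 'much better' considered an optimal outcome") and then names the test: "A chi-square test of association will be used to compare primary outcome (PGI-I) between treatment groups". The SAP adds no model: "Independent samples t test, Mann-Whitney, x2, Wilcoxon signed rank sum statistical tests were used as appropriate". Neither document names a covariate or a stratified test for the primary comparison, and neither gives an effect measure with a confidence interval.

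Three other places bear on this:

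- Protocol section 2.0 (Background) states: "Reduced satisfaction and treatment failure after midurethral sling surgery is associated with higher baseline urgency and urgency incontinence". It gives no effect size.
- Protocol section 6.0 collects the relevant measure before treatment: "All patients will also complete a 3-day urinary diary at baseline quantifying the number of incontinence episodes (stress and urge". The UDI-6 and PGI-S are also taken at baseline.
- Protocol section 14.0 says that randomization is done in REDCap and states no stratification factor.

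Baseline predictors appear only in secondary aim c (section 1.0), which concerns persistent urgency incontinence and not the comparison of arms.

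**The concern.** The protocol itself identifies a prognostic factor, measures it before treatment and then leaves it out of the primary comparison. As far as the documents state, the randomization does not balance it either. In a trial of about 34 evaluable women per arm, baseline urgency can differ noticeably between arms by chance. An unadjusted difference in proportions carries whatever imbalance occurs in that one trial. Adjusting for a covariate that truly predicts outcome would remove most of it and tighten the estimate without adding patients. At stake is some precision, and how credible the estimate looks if the arms turn out to differ on urgency.

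**Working it through.** **1. Reproduce the sample size.** The rates are in the SAP: "Assuming 66% of women in the placebo group and 93% in the onabotulinumtoxinA group were" improved. So is the error specification: 34 per arm "were needed to show a significant difference with 80% power at 0.05 significance level". The protocol's own sentence prints the level differently ("to show a significant difference with 80% power at a 0.5 significance level"). Sidedness is not stated; two-sided is assumed.

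With the pooled-variance formula, no continuity correction and mean rate (0.66 + 0.93)/2 = 0.795:

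n = [1.960 × √(2 × 0.795 × 0.205) + 0.842 × √(0.66 × 0.34 + 0.93 × 0.07)]² / 0.27² = (1.119 + 0.453)² / 0.0729 = 33.9, so **34 per arm**.

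This matches. A level of 0.5 would give 10 per arm, so 0.05 is the level behind the figure. Formula power at 34 is 80.1%. Exact power of the Pearson chi-square is 83.3% at 34 per arm, 87.9% at 39 and 94.7% at 50.

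**2. How many covariates the data can carry.** Expected failures at 34 per arm are 34 × 0.34 = 11.6 on sling alone and 34 × 0.07 = 2.4 on the combination, about 14 in total. That supports one covariate. The chance of no failures in the active arm is 0.93^34 = 8.5%. In those trials a logistic model with a treatment term has no finite estimate, whereas a linear model still gives one.

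**3. Gain from adjusting.** The strength of the covariate is assumed, as the odds ratio for failure per SD of baseline urgency. The other settings are simulated trials with 34 per arm and marginal rates fixed at 66% and 93%. The comparator is the planned chi-square.

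| Odds ratio per SD | Chi-square | Adjusted logistic score test | Adjusted linear model, robust (HC3) errors |
|---|---|---|---|
| 1 | 83% | 83% | 82% |
| 2 | 84% | 86% | 85% |
| 2.7 | 83% | 87% | 86% |

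The change is therefore 0 to +4 points for the score test and -1 to +3 for the linear model. A second run of the linear model put the loss at odds ratio 1 nearer 2 points (83.3% against 81.1%). At odds ratio 1.5, the score test and the chi-square both gave 84.1%.

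The variance of the adjusted risk difference, relative to the unadjusted one, was 1.02 at odds ratio 1, 1.00 at 1.5, 0.96 at 2 and about 0.90 at 2.7. With 66% in both arms, rejection rates were 4.6% to 5.6% for the chi-square and 4.8% to 5.5% for the adjusted score test. They were 3.7% to 5.3% for the linear model.

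At the protocol's 50 per arm, power was 94.6% with either analysis at odds ratio 1.5, and 94.8% against 95.6% at odds ratio 2.

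**4. Size of a chance imbalance.** For a baseline feature present in half the women (assumed), the SD of the between-arm difference at 34 per arm is √(2 × 0.25/34) = 0.121, or 12 points. A difference of 20 points or more has probability 11% at 34 per arm, 9% at 39 and 6% at 50.

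The shift in the risk difference is the imbalance times the gap in success between strata. With assumed gaps of 10, 20 and 30 points, a 20-point imbalance shifts it by 0.20 × 0.10 = 2, 0.20 × 0.20 = 4 and 0.20 × 0.30 = 6 points. The planned difference is 27 points.

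**The case against.** The strongest reply is that nothing here is broken. Under randomization, chance imbalance is already part of the chi-square's null distribution, so its type I error allows for it on average. The sample size was calculated for that test, and correctly.

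The evidence on prognostic strength is also thin. Section 2.0 offers one sentence without an effect size, about slings without the injection. The project abstract in the same section says that it has been hard to tell in advance which women will have persistent or worse urgency incontinence. Aim c treats the predictors as still to be found. The entry rule in section 3.0, which requires one of two bother levels on the UDI urgency and stress items, narrows the spread of baseline bother. If the covariate is weak, the robust linear model loses a little power against the chi-square. At 50 per arm there is little left to gain.

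All of this stands, and it limits the size of the point. It does not remove it. The entry rule restricts questionnaire bother, not diary counts, so urge episodes can still vary widely. The 50-per-arm figure is not the SAP's: 78 women with 15% dropout leave 78 × 0.85 = 66.3 evaluable, just under the 68 required.

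A reader might infer that the unadjusted test is biased, that it leaves the trial open to false positives from imbalance, or that the trial is underpowered without adjustment. The documents support none of these. Nor do they show that the adjusted model must replace the chi-square.

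**Conclusion.** The point holds as one of efficiency and robustness, not as an error. The plan has a plausible prognostic measure at no extra data cost and does not use it. On assumed odds ratios of 1 to 2.7 per SD, a single adjustment at 34 per arm changes power by about -1 to +4 points across the two adjusted methods. It changes the variance of the risk difference by about +2% to -10%, with type I error near 5%. The benefit in a particular trial is larger if the arms happen to differ on urgency, but a 20-point imbalance is uncommon (11%) and would shift the estimate by only 2 to 6 points out of 27.

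These sizes rest on an assumed prognostic strength, the design rates of 66% and 93%, and randomization that is not stratified on urgency; the documents state no stratification but do not rule it out.

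**What to change.** Keep the chi-square as planned, and add to the SAP, before unblinding, one covariate-adjusted analysis of improved PGI-I at 3 months:

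- **Estimate:** the risk difference with a 95% CI, from a linear model with robust standard errors. This stays estimable if the active arm has no failures.
- **Covariate:** log(count + 1) of urge episodes on the baseline 3-day diary, and no other. The offset is needed because eligibility rests on UDI bother, so a zero diary count is possible.
- **Missing baseline count:** impute the overall mean regardless of arm, so that no woman with an outcome is dropped.
- **Status:** state whether this is the primary estimate or the named key supportive analysis, and report the chi-square alongside it.

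The SAP is written in the past tense. If unblinded analysis has already begun, the adjusted result should be labelled post hoc.

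The cost is a few SAP sentences and one extra model, with no additional patients or data. The downside is no gain, or a power loss of about 1 point, if baseline urge episodes prove weakly prognostic. The addition also supplies an effect estimate and interval, which neither document specifies for the primary outcome.
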